8.2. Schedule of Assessments

8.2.1. Site set-up

Centre eligibility

Recruiting centres must have eligible surgeons willing to participate in the LAVA trial such that both laparoscopic and open hysterectomy can be offered for the treatment of benign gynaecological conditions. This mandates that surgeons with specific expertise in either laparoscopic or open hysterectomy within each recruiting centre are prepared to refer patients to surgical colleagues, and vice-versa, according to the type of hysterectomy allocated post-randomisation. Some surgeons considering themselves equally adept in both types of hysterectomy, and who meet the eligibility criteria, will be able to undertake both procedures within the LAVA trial. Surgeons within recruiting centres willing to participate in the LAVA trial comprise the 'Local Surgical Unit' (see 'Expertise Based Process'). They should have at least one surgeon willing to randomise to LAVA and agree local eligibility criteria for undertaking either laparoscopic OR open hysterectomy.

Surgeon eligibility

For a surgeon to be considered expert in a particular type of hysterectomy (laparoscopic or open), minimum standards regarding experience and case load will need to be established as follows:

- A minimum of 30 cases conducted
- Current caseload of at least 12 cases per year.

(Note - these criteria will need to be met for laparoscopic and open hysterectomy for surgeons conducting both procedures in the LAVA trial)

In light of the unprecedented restrictions on elective operating for benign conditions imposed by the Covid 19 pandemic, the required surgical caseload can be determined from the year preceding the SARS-COV-2 viral outbreak in March 2020.

8.2.2. After consent but before randomisation

Baseline demographic and medical data ("Consent and randomisation CRF" - *local research team to complete*)

To include:

- Age
- Ethnicity
- BMI (≤ 29.9 , 30-34.9, ≥ 35 Kg/m²)
- Previous caesarean section (yes / no)
- Uterine Size - ≤ 12 weeks, > 12 weeks
- Planned retention of cervix yes / no

Baseline quality of life, symptom and physical functioning questionnaires (*participant to complete*)

- Patient-Reported Outcomes Measurement Information System Physical Function (PROMIS-PF) item bank v1.2 ("Baseline Personalised recovery CRF")
 - Selection of 8 activities, that in the participants view most reflect their day-to-day activities which will then will be used to assess return to usual activities.
- Baseline quality of life and symptom CRF:
 - Quality of life data (EQ-5D-5L and EQ VAS)
 - Sexual Activity Questionnaire (SAQ)
 - Urogenital Distress Inventory (UDI)
 - Defecatory Distress Inventory (DDI)
 - Pelvic organ prolapse symptom score (POP-SS)

8.2.3. Hospital stay

- Surgical details ("Day of surgery CRF" - *local research team to complete*)
 - to include Clavien-Dindo grade of surgical complications, anaesthetic complications (where applicable), surgical details such as duration, estimated blood loss, conversion to laparotomy, uterine weight
- Resource use ("Day of surgery CRF" and "Post-operative inpatient CRF to complete on discharge" - *local research team to complete*)
 - to include time for procedures, personnel present, equipment usage, time to discharge
- Quality of recovery CRF (Quality of Recovery 15 - QoR-15) at 24 hours post-surgery (*participant to complete*) *Note - if the patient is discharged as a day-case [i.e. within 24 hours] then they should be requested to complete this at home*
- Post-operative pain diary CRF
 - Numerical rating scale (NRS) to measure post-operative pain, and analgesia use (*participant to complete in hospital and / or at home according to the day of discharge post-operatively*)

8.2.4. Days 1-14 after surgery

- Post-operative pain diary CRF
 - Numerical rating scale (NRS) to measure post-operative pain, and analgesia use (*participant to complete in hospital and / or at home according to the day of discharge post-operatively*)

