1. BACKGROUND AND RATIONALE

1.1. Background

Hysterectomy is common, with one in ten women undergoing the procedure in their lifetime, mostly for benign conditions¹⁻³. 30,000 women undergo a hysterectomy every year in the UK for benign indications such as abnormal uterine bleeding and pelvic pain¹⁻³. The procedure is associated with high rates of patient satisfaction and improvement in quality of life (QoL) but serious complications can arise^{4, 5}. The morbidity arising from hysterectomy imposes a burden on women and the ubiquity of the procedure utilises a substantial amount of scarce health care resources⁶⁻⁹. Currently, most hysterectomies are performed abdominally because this traditional method is thought to minimise intra-operative complications but the increased trauma of an abdominal cut can prolong recovery⁵. This may be especially true in overweight and obese women, where morbidity is greater from mobility restrictions and wound infection¹⁰.

Hysterectomy can be performed through large abdominal incisions (abdominal hysterectomy), through small 'key-hole' abdominal incisions (laparoscopic hysterectomy) or via the vagina without any abdominal incisions (vaginal hysterectomy). In contrast to vaginal hysterectomy, which is usually undertaken for uterine prolapse or when the uterus is not enlarged, both abdominal and laparoscopic hysterectomy can be performed in most women with benign disease. The morbidity associated with an abdominal incision, in particular wound infection and pain, has meant that abdominal hysterectomy requires longer inpatient stay and recovery times compared with laparoscopic hysterectomy. On the other hand, laparoscopic hysterectomy takes longer to perform, requires specialist surgical skills and is associated with more urological complications compared with traditional abdominal hysterectomy⁴.

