8.2.9. At home week 12/24/36 months post-surgery* **

- 12/24/36 month post-hysterectomy CRF
 - Satisfaction with hysterectomy (5-point Likert scale ranging from very satisfied to very unsatisfied), assessment of new gynaecological symptoms, symptoms of urogenital prolapse (pelvic organ prolapse quantifications – POP-SS bladder function using Urogenital Distress Inventory (UDI), bowel function using Defecatory Distress Inventory (DDI) questionnaire, sexual function using the Sexual Activity (SAQ) questionnaire, quality of life score using EuroQol-5D-5L questionnaire and VAS, body image using the Body Image Scale (BIS) questionnaire,

contact with Community Social and Clinical Care Services and time away from normal activities.

*The latter two time-points will only be collected for participants who reach these times prior to the study closes after all participants have been followed up for 12 months.

**Participants will be offered the option to complete these questionnaires online, via a link sent to them in a text message. Participants will receive reminders to complete their questionnaires

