13. STATISTICAL CONSIDERATIONS

13.1. Sample Size

To enable 90% power to test the non-inferiority hypothesis at a one-sided 2.5% significance level (two-sided 5% level) assuming a 3% margin of non-inferiority and a major surgical complication rate of 6% in the abdominal (control) group requires 2634 participants. The estimate of 6% is taken from a similar previous comparative study.¹¹ A 3% margin is justifiable because of the trade-off of potentially swifter recovery with laparoscopic surgery; a view shared by our patient focus group and is substantially less than the 5% difference observed in the previous major trial,¹¹ which led to the continued use of open abdominal hysterectomy.

An extra consideration is the potential for clustering by surgeon due to the expertise based design.^{19 34} Under the assumption that each of the 50 centres will utilise 6 surgeons (operating on approximately 9 patients on average during the study), along with an intra-cluster correlation (ICC) estimate of 0.02, the sample size has been increased by 16% to 3055. This ICC estimate used - in the absence of precise estimates - is considered conservative given the outcome is clinical and of low prevalence, both of which are factors associated with low ICC.^{35, 36} However, even varying these factors up to an ICC of 0.07 or average cluster size of 29, shows we will have at least 80% power to establish non-inferiority in these situations.

A final inflation of 6% to account for loss to follow-up (similar to the aforementioned previous study) brings the final sample size total to 3250 participants. This size of sample would give the ability to detect meaningful differences between groups in our key secondary outcome of time from surgery to resumption of usual activities. Assuming the median recovery time in the abdominal group is between 6 and 9 weeks³⁷ we will have high levels of power (>90%) to detect reductions of 1 week in all cases.

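### The Body Image Scale and the post-operative pain score have no pre-randomisation value, so their exploratory arm comparisons stay unbiased but lose some precision

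*Protocol*

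**What the plan says.** Section 8.2.2 lists what women complete before randomisation under "Baseline quality of life, symptom and physical functioning questionnaires". The list holds the PROMIS-PF activity selection, EQ-5D-5L with its visual analogue scale, SAQ, UDI, DDI and POP-SS. It contains neither a pain numerical rating scale (NRS) nor the BIS.

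The schedule in 8.2.10 agrees. UDI, DDI, SAQ, EQ-5D-5L and POP-SS are marked at baseline. Pain NRS is marked only for the hospital stay and days 2 to 14, and BIS only at month 12 (repeated at 24 and 36 months where reached).

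The outcome sections match. Section 8.2.4 has the "Numerical rating scale (NRS) to measure post-operative pain, and analgesia use", and the 12-month form in 8.2.9 includes "body image using the Body Image Scale (BIS) questionnaire".

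Section 13.2.2 compares both between arms by linear regression: pain NRS is named, and BIS falls under the participant-reported questionnaires. Section 13.2 names only the minimisation variables as covariates and treats secondary outcomes other than the key one as exploratory. Section 1.1 says hysterectomy is done "for benign indications such as abnormal uterine bleeding and pelvic pain", and 3.2 lists pelvic pain clinics among the places of recruitment.

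**The concern.** Some women will have pelvic pain or disturbed body image before the operation. Those differences carry into the follow-up score. If no pre-operative score is held, they stay in the residual variance. The minimisation variables (previous caesarean section, BMI, uterine size, planned cervical retention, centre) do not measure pain or body image directly, so they cannot be relied on to remove this variation.

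Choice of covariates can be left to a statistical analysis plan, but collection of the score cannot. No analysis plan can adjust for a BIS value that was never taken, and the assessment schedule is fixed in the protocol. At stake is the width of the intervals for two exploratory outcomes.

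**Working it through.** **1. The protocol's own sample size.** Section 13.1 opens with the error rates: "To enable 90% power to test the non-inferiority hypothesis at a one-sided 2.5% significance level". The remaining inputs and the resulting total are then given as follows: "assuming a 3% margin of non-inferiority and a major surgical complication rate of 6% in the abdominal (control) group requires 2634 participants". With equal true rates:

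n per arm = 2 × 0.06 × 0.94 × (1.960 + 1.282)² / 0.03² ≈ 1317, so N = 2634. This reproduces.

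The clustering step takes a mean of about 9 women per surgeon. Its second input and its result are stated thus: "along with an intra-cluster correlation (ICC) estimate of 0.02, the sample size has been increased by 16% to 3055". Design effect = 1 + (9 − 1) × 0.02 = 1.16, and 2634 × 1.16 = 3055. With 6% loss, 3055 / 0.94 = 3250. Both reproduce. The point raised here does not touch these figures. The protocol gives no SD, target difference or power for NRS or BIS.

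**2. Half-width without a baseline score.** Taking 3055 analysed and the 1.16 design effect, the effective number per arm is 3055 / 1.16 / 2 ≈ 1317.

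Half-width = 1.96 × √(2/1317) = 0.076 SD. Leaving out the design effect would give 1.96 × √(2/1527.5) = 0.071 SD, which is optimistic under the protocol's own clustering assumption.

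**3. Effect of a baseline covariate.** Residual variance is multiplied by 1 − r², and interval width by √(1 − r²). Here r is the baseline/follow-up correlation, strictly the part left after the minimisation variables. It is an assumption.

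| r | 1 − r² | √(1 − r²) | Interval narrower by | Half-width (SD) |
|---|---|---|---|---|
| none | 1.00 | 1.000 | – | 0.0764 |
| 0.1 | 0.99 | 0.995 | 0.5% | 0.0760 |
| 0.2 | 0.96 | 0.980 | 2.0% | 0.0748 |
| 0.3 | 0.91 | 0.954 | 4.6% | 0.0729 |
| 0.5 | 0.75 | 0.866 | 13.4% | 0.0662 |
| 0.6 | 0.64 | 0.800 | 20.0% | 0.0611 |

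**4. What that means for detection.** At an effective N of 2634, the difference detectable with 90% power is 0.126 SD without a baseline. It becomes 0.120 SD at r = 0.3, 0.109 SD at 0.5 and 0.101 SD at 0.6. Power for a 0.10 SD difference goes from 73% to 77%, 84% or 89%. Power for 0.20 SD is already 99.9% without a baseline.

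**5. If the change comes after recruitment has started.** Suppose a share f of women have a baseline value and the rest are given the mean. The variance explained is then f × r². For illustration, with f = 0.5 and r = 0.5, this is 0.125, and the interval narrows by 1 − √0.875 = 6.5% instead of 13.4%.

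**The case against.** The text and the schedule agree with each other, so the protocol does not contradict itself. QoR-15 and WPAI also lack a baseline. The design can therefore be read as taking early-recovery and work measures only after surgery and standing symptom scales at both times. That reading is reasonable for the pain NRS, which is defined as post-operative pain over at most 14 days. It does not cover BIS, which sits at 12 months beside five instruments that all have a baseline.

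The correlation is undocumented. For pain it may well be low: a single pre-operative rating, in women whose pain may be cyclical, is set against pain from the operation itself. This stands, and is why the range starts at r = 0.1. Baseline EQ-5D-5L also already covers pain in part, so a separate NRS item would add only what goes beyond that. Nothing collected at baseline measures body image in the same way.

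Burden is a fair point. The pack already holds five instruments plus the choice of 8 activities from 29, and 6.3 makes randomisation wait for baseline items.

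A reader might go further than the documents allow in three ways:

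- **Bias.** The absence of a baseline does not bias the arm comparison, because allocation is randomised.
- **Change scores.** A 12-month BIS score alone does not show change since surgery, but the protocol plans no within-woman change analysis.
- **Inconsistent adjustment.** The protocol does not say that UDI, DDI, SAQ, POP-SS or EQ-5D-5L will be adjusted for their baselines, so BIS and pain are not denied an adjustment promised to the others. The difference lies in what is collected.

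**Conclusion.** The point holds as a small and avoidable loss of precision, stronger for BIS than for pain. Both comparisons are unbiased. For BIS, at an assumed r of 0.5 to 0.6, the interval would be 13 to 20% narrower with a baseline covariate. For acute post-operative pain, at r = 0.1 to 0.3, the gain is about 0.5 to 5%.

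The percentages depend only on r. The half-widths in SD units also assume 3055 women analysed and the design effect of 1.16. Both figures were set for the primary outcome, and actual diary and 12-month return rates or surgeon clustering may differ.

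It would be wrong to read this as a power problem. The sample size was driven by the complication outcome, these two outcomes are exploratory, and even unadjusted the trial can detect small differences in either. No main conclusion depends on it.

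**What to change.** - Add the BIS to the baseline quality-of-life and symptom CRF in 8.2.2, mark it at baseline in 8.2.10, and use it as a covariate in the linear model for 12-month BIS.
- Optionally add one 0–10 pain NRS item to the same form, for use in the pain model.
- In any case, adjust the pain NRS model for the baseline EQ-5D-5L pain/discomfort level. This needs no new data.
- For women randomised before the change, keep them in the analysis with the mean imputed for the missing baseline covariate.

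The cost is one short questionnaire, and at most one further item, on a form women already complete. This adds slightly to the burden before randomisation. Women already enrolled will have no baseline value, so the gain shrinks the later the change is made. If the sponsor prefers not to add the BIS, a sentence giving the reason would settle the point.

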8.2.5. Week 6 after surgery

- Six week follow up CRF
 - Post-surgery complication and representation form (*local research team to complete*)

8.2.6. At home weeks 1 to 26

- Patient-Reported Outcomes Measurement Information System Physical Function (PROMIS-PF) item bank v1.2
 - Patient to record the date when each of her 8 pre-selected physical activities is achieved using a text application that provides a link to the questionnaire on the BCTU trial database. Until attainment of all 8 pre-selected criteria participants will receive weekly text reminders to complete the PROMIS-PF during the first 12 weeks, fortnightly from 13 to 26 weeks after which requests will cease. It is anticipated that most participants will have resumed all their pre-selected activities between 6 and 9 weeks post-surgery (*participant to complete*).

8.2.7. At home week 6 post-surgery **

- Quality of life score and work assessment ("6 week follow up CRF")
 - EuroQol-5D-5L and VAS
 - Use of health services
 - Time away from normal activities

8.2.8. At home week 12 post-surgery **

- Quality of life score and work assessment ("12 week follow up CRF")
 - EuroQol-5D-5L and VAS
 - Time from surgery to work (if working) and work productivity and activity impairment scores using WPAI-GH questionnaire

8.2.9. At home week 12/24/36 months post-surgery* **

- 12/24/36 month post-hysterectomy CRF
 - Satisfaction with hysterectomy (5-point Likert scale ranging from very satisfied to very unsatisfied), assessment of new gynaecological symptoms, symptoms of urogenital prolapse (pelvic organ prolapse quantifications – POP-SS bladder function using Urogenital Distress Inventory (UDI), bowel function using Defecatory Distress Inventory (DDI) questionnaire, sexual function using the Sexual Activity (SAQ) questionnaire, quality of life score using EuroQol-5D-5L questionnaire and VAS, body image using the Body Image Scale (BIS) questionnaire,

contact with Community Social and Clinical Care Services and time away from normal activities.

*The latter two time-points will only be collected for participants who reach these times prior to the study closes after all participants have been followed up for 12 months.

**Participants will be offered the option to complete these questionnaires online, via a link sent to them in a text message. Participants will receive reminders to complete their questionnaires

8.2.10. Summary of schedule of assessments

Visit	Pre-randomisation		Rand	Surgery	Post-surgery						
	Screening and recruitment	Baseline		Surgery	Hospital stay	Day 2-14	Weekly Week 1 to 12 (inc)	6 weeks + 28 days	12 weeks + 28 days	Fortnightly weeks 13 to 26 (inc)	Month 12 + 6 months **
Eligibility check	x										
Valid informed consent	x										
Baseline demographic and medical questionnaire		x									
Urogenital Distress Inventory (UDI)		x									x
Defecatory Distress Inventory (DDI)		x									x
Sexual Activity Questionnaire (SAQ)		x									x
EuroQol (EQ-5D-5L and EQ VAS)		x						x	x		x
Patient-Reported Outcomes Measurement Information System Physical Function (PROMIS-PF)		x					x			x	
Randomisation			x								
Surgery CRF				x							
Resource use CRF					x						

Pain (Numerical Rating Scale - NRS) & analgesia questionnaire					X						
Time to discharge & complications					X						
Quality of Recovery-15 questionnaire*					X						
Pain (NRS) symptom diary						X					
Six week post-surgery questionnaire including health care utilisation								X			
Work questionnaire / Work Productivity and Activity Impairment Questionnaire (WPAI-GH)									X		
Six week post-surgery complication and representation form								X			
Satisfaction with hysterectomy											X
New gynae symptoms											X
Pelvic organ prolapse quantifications – POP-SS		X									X
Body Image Scale (BIS)											X
Contact with Community Social and Clinical Care Services form											X
Serious Adverse Events				X	X	X	X	X	X	X	X

* *If patient discharged as a day-case then they should be instructed to complete at home at 24 hours post-surgery*

****** *The same 12 month post-surgery questionnaires will be sent to all participants reaching 24 and 36 months of follow up post-surgery, prior to close of the LAVA study; defined as when the last randomised patient reaches 12 months follow up post-surgery*

8.3. Participant Withdrawal

Informed consent is defined as the process of learning the key facts about a clinical trial before deciding whether or not to participate. It is a continuous and dynamic process and participants should be asked about their ongoing willingness to continue participation.

Participants should be aware at the beginning that they can freely withdraw (discontinue participation) from the trial (or part of) at any time.

LAVA has adopted an analysis based on a modified intention to treat principle, i.e. all participants will be followed up and analysed in the treatment group to which they were randomised provided a hysterectomy (of any type) was undertaken unless they withdraw from the study.

Types of withdrawal as defined are:

- a) If for any reason the participant has not undergone a hysterectomy of any type they will be considered to have withdrawn from the study and not be followed up
- b) The participant would like to withdraw from the allocated trial treatment pathway but is still having a hysterectomy of any type, and does not wish to attend trial visits in accordance with the schedule of assessments but is willing to be followed up at standard clinic visits and if applicable using any central UK NHS bodies for long-term outcomes (i.e. the participant has agreed that data can be collected at standard clinic visits and used in the trial analysis, including data collected as part of long-term outcomes)
- c) The participant would like to withdraw from trial treatment but is still having a hysterectomy of any type, and is not willing to be followed up in any way for the purposes of the trial and for no further data to be collected (i.e. only data collected prior to the withdrawal can be used in the trial analysis)

or

- d) The participant wishes to withdraw completely from the trial (i.e. from trial treatment and all follow up) and is not willing to have any of their data, including that already collected, to be used in any future trial analysis

*If the participant wishes to withdraw from the allocated trial treatment pathway but is still having a hysterectomy of any type, and is willing to be followed up in accordance with the schedule of assessments and if applicable using any central UK NHS bodies for long-term outcomes (i.e. the participant has agreed that data can be collected and used in the trial analysis), they will **not** be considered as being withdrawn from the study*

The details of withdrawal (date, reason and type of withdrawal) will be clearly documented in the source data.

